## **Trial design:**

The trial is a randomised, multi-centre, multinational, placebo-controlled, double-dummy, doubleblind, efficacy, safety and pharmacokinetic clinical proof of principle (CPOP) trial in subjects with newly diagnosed T1DM. The trial includes four parallel treatment groups, one with NNC0114-0006 12 mg/kg intravenously every 6 week and liraglutide 1.8 mg subcutaneously daily, one with NNC0114-0006 12 mg/kg intravenously every 6 week, one with liraglutide 1.8 mg subcutaneously daily, and, one placebo arm randomised in a even ratio. The liraglutide dose may be reduced to 1.2 mg, if 1.8 mg is not tolerated. Subjects will continue their pre-trial insulin treatment.

The randomisation will be stratified according to the non-fasting C-peptide value at screening. The stratification factor has two levels according to C-peptide value:  $\geq 0.2 \text{ nmol/l to } \leq 0.6 \text{ nmol/l and } > 0.6 \text{ nmol/l}$ .

The exposure period for NNC0114-0006 and liraglutide in combination or alone is 54 weeks followed by a 26 weeks observation period. All groups will receive insulin treatment according to a treat-to-target regimen throughout the entire trial.

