#### 8.5.1 Laboratory assessments for efficacy

#### 8.5.1.1 Glucose metabolism

The following will be analysed:

- $HbA_{1c}$  will be measured according to Section 2, except at Visit 1.
- Fasting plasma glucose (FPG) will be measured according to Section 2, except at Visit 1. For the measurement of FPG the subject must be fasting according to Section 8.1.8.
- Fasting glucagon will be measured according to Section 2, except at Visit 1. For the measurement of fasting glucagon the subject must be fasting according to Section 8.1.8.
- Fasting C-peptide will be measured according to Section 2, except at Visit 1. For the measurement of C-peptide the subject must be fasting according to Section 8.1.8.
- PG (non-fasting) will be measured at Visit 1.
- C-peptide (non-fasting ) will be measured at Visit 1.

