$ln(AUC_{0-4h, C-peptide, baseline})$	fixed effect covariate with a visit dependent coefficient
Visit	fixed effect factor corresponding to time t=12w, 24w, 36w, 54w
Treatment	fixed effect interaction term between treatment and visit (i.e. the treatment effect is not assumed the same for all visits), with treatment as a factor with 4 levels: NNC0114-0006 in combination with liraglutide, NNC0114-0006, liraglutide and placebo
Stratum	fixed effect interaction term between stratum and visit, with stratum as a factor with two levels according to non-fasting C-peptide measurement at screening: 0.2-0.6 nmol/l and >0.6 nmol/l
Age	fixed effect covariate with a visit dependent coefficient
Sex	fixed effect interaction term between sex and visit

 Table 17–2
 Model terms for the statistical model for the primary endpoint

The variance-covariance matrix for the repeated measurements for each subject will be unstructured and may depend on treatment, if an assumption of equal variance-covariance matrix between treatments turns out not to be reasonable.

From the model, least square means (LSMeans) for each treatment group at selected time points, including week 54 will be estimated, and mean differences between treatment groups in log-transformed  $AUC_{0-4h, C-peptide,\Delta t}$  at these time points will be estimated. These estimates will be back-transformed to the original scale to represent treatment (geometric) means and treatment (geometric mean) ratios with 95% CIs.

The primary endpoint will be summarised using descriptive statistics and presented graphically.

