Several subjects have failed to fulfil inclusion criterion 4 due to not fulfilling the requirement of being non-fasting, which may result in a lowering of the subjects C-peptide result. To mitigate this, the measurement of non-fasting C-peptide will be moved to Visit 2 at which the first MMTT is performed. By having the stimulated C-peptide level at Visit 2 during the MMTT above or equal to 0.2 nmol/l the eligible subjects will have the desired beta cell function, and excluding possibly eligible patients, who were fasting at Visit 1, will be avoided.

Termination of bolus insulin use is a good measure of the quality of life of the participating subjects. In order to measure this, an additional secondary endpoint has been introduced in section 4.2.2.1 assessing the number of subjects no longer using bolus insulin. Further, section 5.3.3 has been updated based on this additional endpoint. This end-point should ideally have been

Protocol Amendment 2	Date:	14 March 2016	Novo Nordisk
Trial ID: NN9828-4150	Version:	1.0	
UTN: U1111-1154-7172	Status:	Final	
EudraCT No.: 2014-001215-39	Page:	5 of 27	

implemented from start trial. Data from >200 subjects, will however provide important data from a clinical important parameter.

The INS DNA assay was hypothesized to identify waves of beta-cell death by measuring the ratio of methylated to un-methylated insulin DNA, thus providing a method of assessing beta-cell loss. No functioning assay for analysing differential INS DNA has been developed and it is hence decided to exclude this assessment from the protocol in section 4.2.2.3 and 8.5.1.3.

Treatment with liraglutide and insulin has been clarified in section 5.3.2 and section 5.3.3 with regards to escalation and missed doses.

Maximum number of subjects to be randomised has been deleted in section 1 and section 6.1 to avoid screened failing subjects due to maximum randomisation number met. The period between screening and randomisation is up to 4 weeks and screening in IV/WRS will be monitored very closely when the planned number of randomised subjects is approaching. The current screen failure rate will be considered when the decision of closing screening is taken.

Exclusion criteria 16, 21 and 39 have been updated in section 6.3 for clarification based on questions from participating sites. These changes have no medical or scientific impact on the criteria.

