#### **Trial Design**

The *rR* and omisation will be stratified according to the non-fasting *peak* C-peptide value at screening *Visit 2*.

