**Table 2-2 Model terms for the statistical model for the primary endpoint**

Model term	Description
$\ln(y_{it})$	dependent variable, subject i, time t
$\ln(\text{AUC}_{0-4h, \text{ C-peptide}, \text{ baseline}})$	fixed effect covariate with a visit dependent coefficient
Visit	fixed effect factor corresponding to time t=12w, 24w, 36w, 54w
Treatment	fixed effect interaction term between treatment and visit (i.e. the treatment effect is not assumed the same for all visits), with treatment as a factor with 4 levels: NNC0114-0006 in combination with liraglutide, NNC0114-0006, liraglutide and placebo
Stratum	fixed effect interaction term between stratum and visit, with stratum as a factor with two levels according to non-fasting max C-peptide measurement during MMTT at Visit 2: 0.2-0.6 nmol/l and >0.6 nmol/l
Age	fixed effect covariate with a visit dependent coefficient
Sex	fixed effect interaction term between sex and visit

The variance-covariance matrix for the repeated measurements for each subject will be unstructured.

From the model, least square means (LSMeans) for each treatment group at selected time points, including week 54 will be estimated, and mean differences between treatment groups in log-transformed  $\text{AUC}_{0-4h, \text{ C-peptide}, \Delta t}$  at these time points will be estimated. These estimates will be back-transformed to the original scale to represent treatment (geometric) means and treatment (geometric mean) ratios with 95% CIs.

The primary endpoint will be summarised using descriptive statistics and presented graphically.

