- The description of the stratification variable has been updated from non-fasting C-peptide measurement at screening to non-fasting peak C-peptide measurement during MMTT at Visit 2 in alignment with protocol amendment 2.
- In the analysis of the primary endpoint, it has been deleted, that the variance-covariance matrix may depend on treatment, if an assumption of equal variance-covariance matrix between treatments turns out not to be reasonable. Instead it has been included that a sensitivity analysis where the variance-covariance matrix depends on treatment will be added if an assumption of equal variance-covariance matrix between treatments turns out not to be reasonable.

- Update of the first sensitivity analysis to specify that it is the endpoints calculated from MMTT stopped before 4 hours due to hyperglycaemia or hypoglycaemia that are excluded from the analysis, and not all the data for that subject.
- Sensitivity analysis added where endpoints calculated from MMTT profile that includes imputed values is excluded.
- Sensitivity analysis added where endpoints calculated from the MMTT, where the date of the MMTT is more than one day after the last liraglutide dosing is excluded.
- In the analysis exploring the effect of the different biomarkers on primary endpoint, the description of the analysis for categorical biomarkers has been deleted, as all biomarkers are continuous.
- In the exploratory analysis that investigates a potential effect of the concentration of liraglutide on the primary endpoint, it has been specified that the liraglutide concentration should be measured at the date corresponding to the MMTT, and not just the visit corresponding to the MMTT. The specification is done as the MMTT can be re-scheduled within 1-10 days.
- In alignment with the endpoint description in Section [1.1.2.2](#), it is specified that the endpoint for total daily insulin dose is derived per kg body weight.
- As only the insulin doses prior to visit 3, 63 and 89 will be transferred from the eDiary (as per the trial data handling plan), the description of the endpoints has been updated, and the statistical analysis has been changed from a MMRM to a normal regression model:
  - The total daily insulin dose will be derived as the average of the doses reported on the three days prior to visit 3, 63 and 89.

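### The SAP's stratum is the Visit 2 peak C-peptide for everyone, so for subjects randomised before Amendment 2 took effect the model term is not their randomisation stratum

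*SAP*

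**What the plan says.** Two definitions of the stratum governed randomisation at different times, both cut at 0.6 nmol/l.

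- **Protocol version 2.0 (7 May 2015).** The Summary states: "The randomisation will be stratified according to the non-fasting C-peptide value at screening". Section 8.5.1.1 gives the sample: "C-peptide (non-fasting ) will be measured at Visit 1". The primary model in Section 17.3 used the same factor, "with stratum as a factor with two levels according to non-fasting C-peptide measurement at screening". Design and analysis agreed.
- **Amendment 2 (14 March 2016).** Because some subjects had not been non-fasting at Visit 1, "the measurement of non-fasting C-peptide will be moved to Visit 2 at which the first MMTT is performed". The Summary's stratification sentence was changed to the peak value at Visit 2, and Section 6.2 defines the peak as the highest of the 11 MMTT samples.
- **SAP.** Table 2-2 carries one definition, "with stratum as a factor with two levels according to non-fasting max C-peptide measurement during MMTT at Visit 2", and Section 2.2 puts all randomised subjects in the full analysis set. Section 3 records the change: "The description of the stratification variable has been updated from non-fasting C-peptide measurement at screening to non-fasting peak C-peptide measurement during MMTT at Visit 2", described as alignment with Amendment 2.

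The SAP has no rule for subjects randomised under the Visit 1 definition, and none of the sensitivity analyses in Section 2.3 addresses it. The same stratum factor is reused in the LOCF and completer analyses, the treatment-by-stratum analysis, and the models for insulin dose, HbA1c, FPG, hypoglycaemia and eGFR.

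**The concern.** When randomisation is restricted within strata, the usual rule is to adjust for those strata. For later subjects the SAP does so. For earlier subjects it substitutes a different measurement: the highest of 11 stimulated samples in place of one sample that, by the sponsor's own account, could be lowered by fasting. Some subjects will fall on opposite sides of 0.6 nmol/l under the two measures, and probably more often upward than downward.

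Three things are at stake.

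- The adjustment term no longer matches the allocation for part of the trial.
- The treatment-by-stratum analysis presents as randomisation strata some groups within which early subjects were not randomised.
- The factor has a coverage gap. Before Amendment 2 the 0.2 nmol/l entry limit applied to the Visit 1 sample, and Protocol Section 8.3.1 allows an MMTT to be reported as not done. An early subject with a Visit 2 peak below 0.2 nmol/l, or with no Visit 2 MMTT, fits neither level (0.2-0.6, >0.6). A subject without that MMTT has no baseline AUC and leaves the primary model anyway, but could still contribute to the secondary models if the stratum were defined.

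**Working it through.** **1. The plan's own figure.** Inputs from SAP Section 2.1: preservation 98% against 65%, SD 0.5 and 1 on the log scale, 60 completers per arm, two-sided 5%.

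- Difference: ln(0.98/0.65) = 0.4106.
- Standard error: sqrt((1² + 0.5²)/60) = 0.1443.
- Power: 0.812 by the normal approximation, 0.803 by the noncentral t with Satterthwaite degrees of freedom, 0.806 with 118 degrees of freedom. Stated: 0.804. Reproduced.
- Numbers: 60/(1 - 0.21) = 75.9, so 76 per arm and 4 × 76 = 304.

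The power calculation contains no stratum term, so the definition of stratum cannot change 0.804 or 304.

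**2. How many subjects are early?** The documents give no count. Amendment 2 expects data from more than 200 subjects for the newly added endpoint on weeks off bolus insulin. If that means subjects randomised from then on, the earlier group is fewer than 304 - 200 = 104, or 104/304 = 34%. There is no documented lower bound; 10% is assumed below. The changeover also depends on local approval (Protocol Section 25), so it need not be one date.

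**3. How many would change stratum?** The documents give no correlation between the two measures, so these rates are assumptions.

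- Bivariate normal measures, both split at the median: discordance = arccos(ρ)/π, which is 25.3% for ρ = 0.7 and 14.4% for ρ = 0.9.
- A simulation with latent log-SD 0.5, measurement noise 0.35 and 0.2, and the peak shifted up by 0 to 40%: 22-29%.

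Range: 14-29% of early subjects. Share of the whole trial: 0.10 × 14% = 1.4% up to 0.34 × 29% = 9.9%.

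**4. Effect on the primary comparison.** Simulation of combination against placebo, 60 per arm, SD 0.5 and 1, blocks of four within strata. Settings: 10%, 26% or 34% of subjects stratified on screening; ρ = 0.7 or 0.9; slope 0.3 on standardised baseline; separate effect of the screening stratum 0 or 0.3; baseline value always in the model; 3,000 trials per setting.

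| Stratum in model | Type I error | Power at 98% vs 65% |
|---|---|---|
| Visit 2 for all | 0.042-0.056 | 0.786-0.813 |
| As randomised | 0.044-0.056 | 0.786-0.812 |

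The largest difference in power between the two in any one setting is 0.6 percentage points (0.787 against 0.794). Monte Carlo error is about 0.4 points for type I error (sqrt(0.05 × 0.95/3000)) and 0.7 points for power (sqrt(0.8 × 0.2/3000)), so the two choices cannot be told apart. This was a single-visit, two-arm regression rather than the four-arm MMRM.

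**5. Where baseline AUC does not help.** The insulin dose, HbA1c, FPG, hypoglycaemia and eGFR models do not list baseline C-peptide AUC. There, stratum is the only C-peptide adjustment, and a subject with no level in it has no defined place.

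**The case against.** The strongest defence is that the SAP's choice is deliberate and reasonable. It was recorded in SAP Section 3 before the randomisation code break, it follows Amendment 2, and the sponsor gave a reason: the Visit 1 sample was sometimes taken fasting. One uniform, better-measured factor is easier to interpret than a variable that pools a single Visit 1 value with an MMTT peak under the same 0.6 nmol/l cut. Log baseline AUC, with a visit-dependent coefficient, already carries the baseline C-peptide information. Nor can it be held against the SAP that its stratum overlaps with that covariate: for later subjects the Visit 2 peak is the randomisation stratum, and the as-randomised factor overlaps just as much.

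Most of this stands. It disposes of any claim about the primary result, and it supports the Visit 2 split for describing subgroups. It does not explain why the adjustment term should drop the factor used to allocate the early subjects, and it leaves the coverage gap open.

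Two stronger readings are tempting. A reader might infer that the mismatch biases the primary estimate or spoils its standard error; the comparison under working shows no such effect. A reader might also take the first 80 randomised subjects as the number enrolled before Amendment 2. In that amendment 80 is a PK sampling target, 20 per arm to yield about 13 full profiles, and not a count of early subjects.

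**Conclusion.** The mismatch is real and can be read directly from the documents: for subjects randomised under the Visit 1 definition, the SAP's stratum is not the randomisation stratum, and no rule covers an early subject who fits neither level. Its practical weight is small. The effect on the primary analysis is negligible under every setting tried. The 1-10% of subjects with a changed stratum rests on an assumed early share of 10-34% and an assumed discordance of 14-29%. Only the upper limit on the early share has support in the documents, and that is itself an inference. What remains is an alignment of analysis with design that matters mainly for the treatment-by-stratum analysis and for the secondary models without baseline C-peptide AUC. It is a free improvement, not a threat to the trial's conclusion.

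**What to change.** Before the randomisation code is broken:

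- In Table 2-2, and in every model that reuses it, define stratum as the stratum recorded in the IV/WRS at randomisation. Leave log baseline AUC as it is.
- In the treatment-by-stratum analysis, keep the as-randomised stratum as the adjustment term and use the uniform Visit 2 peak split for the interaction, labelled as a baseline subgroup. Word its lower level so that a value below 0.2 nmol/l has a place.
- Report how many subjects were randomised under each definition and how many differ between the two.
- Keep the Visit 2 stratum for all subjects as a sensitivity analysis of the primary endpoint.

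The cost is one line of SAP wording, a short clarification of the exploratory analysis, two counts and one extra model run. No new data are needed. That the IV/WRS holds each subject's stratum is inferred from Protocol Section 11, which runs the stratified randomisation through that system.

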### 1.1.1 Objectives

#### Primary objective

The primary objective is to evaluate the effect of NNC0114-0006, liraglutide, and the combination of NNC0114-0006 and liraglutide, compared to placebo, on preservation of beta-cell function after 54 weeks of treatment in adult subjects with newly diagnosed type 1 diabetes mellitus (T1DM).

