## 2 Statistical considerations

Based on the statistical model, treatment means or geometric means (LSMeans) and treatment comparisons (i.e. treatment differences or treatment ratios) will be presented with 95% confidence intervals (CI) and p-values for the two-sided test of no treatment difference. A significance level of

5% will be used. All pairwise treatment differences (or ratios) will be presented. No adjustment for multiple testing will be performed.

Some endpoints will be summarised for the treatment period, for the observation period and for the entire trial period (i.e. the treatment period together with the observation period)

The treatment period and the observation period will be derived for completed subjects as

- The start of the treatment period will be the date of first trial product administration
- The end of the treatment period will be the date of the visit at week 54 (i.e. the day of visit 63)
- The start of the observation period will be the day after the end of the treatment period
- The end of the observation period will be the date of the last visit

For withdrawn subjects the date of last contact will be the maximum of the date of the last visit and the withdrawal date. The treatment period and the observation period will be derived for withdrawn subjects as

- The start of the treatment period will be defined as described for completed subjects
- The end of the treatment period will be as defined for completed subjects if this date is before or on the date of last contact. Otherwise the end of the treatment period will be the date of last contact
- An observation period will only be defined if the date of last contact is after the end of the treatment period
  - The start of the observation period will be defined as for completed subjects
  - The end of the observation period will be the date of last contact

For endpoints evaluated as change from baseline and/or for baseline adjustment in the statistical analyses, baseline will be defined as the information recorded at the Visit 3 (randomisation). If no measurement is available at Visit 3, then the information recorded at Visit 2 will be used as the baseline. Furthermore, if no measurement is available at Visit 2, then the information recorded at Visit 1 will be used as the baseline.

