## 2.1 Sample size calculation

This is a phase 2 trial and the first Novo Nordisk trial of NNC0114-0006 in subjects with newly diagnosed T1DM. Therefore the knowledge on treatment effects and on the standard deviation of the primary endpoint is limited.

The statistical power calculations have been done under the following assumptions

- The primary endpoint is  $AUC_{0-4h}$  for a MMTT stimulated C-peptide concentration-time curve at week 54 relative to baseline, i.e.  $AUC_{0-4h, C-peptide, 54w} / AUC_{0-4h, C-peptide, baseline}$ . The primary endpoint will be log-transformed in the statistical analysis and this will be denoted  $\ln(AUC_{0-4h, C-peptide, \Delta 54w})$ . Thus,  $AUC_{0-4h, C-peptide, \Delta 54w}$  is the proportion of  $AUC_{C-peptide}$  that is preserved after 54 weeks relative to the level at baseline. E.g. a reduction of  $AUC_{C-peptide}$  of 35% corresponds to a preservation of 65% and value of the  $\ln(AUC_{0-4h, C-peptide, \Delta 54w})$  is  $\ln(0.65) = -0.431$ .
- The residual standard deviation of  $\ln(AUC_{0-4h, C-peptide, \Delta 54w})$  in the model described above may depend on the treatment. Based on the results of Herold et al. the standard deviation is assumed to be 1 in the placebo group and 0.5 in the group treated with NNC0114-0006 in combination with liraglutide.
- The expected preservation in the placebo treated patients is 65%, based on the results of Herold et al. who found a mean of 70% decline in  $AUC_{C-peptide}$  over a 24-months period. Assuming a linear decline, the mean 12-months decline would be 35%, i.e. a preservation of 65%. The statistical power calculations have been done assuming three levels of treatment effects for NNC0114-0006 in combination with liraglutide; a preservation of 85% and 95% and 98%, respectively.

[Table 2-1](#) shows the statistical power for the test of no treatment effect if the true mean preservation is 85%, 95% or 98% in the group treated with NNC0114-0006 in combination with liraglutide and 65% in the placebo group when the numbers of completers are 40, 60 or 80, respectively using a two-sided test and 5% level of significance. The rows corresponding to the chosen number of (completing) subjects are highlighted.

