**Table 2–1 Power calculations**

True treatment effect (preservation)	N (completers per group)	Statistical power
85%	40	0.320
85%	60	0.451
85%	80	0.566
95%	40	0.561
95%	60	0.740
95%	80	0.854
98%	40	0.628
98%	60	0.804
98%	80	0.903

Assuming a preservation of 98% and a SD of 0.5 for NNC0114-0006 in combination with liraglutide and a preservation of 65% and a SD of 1 for placebo, then the power will be 80.4% with 60 subjects completing the trial in each of the two treatment arms.

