### Sensitivity analyses of the primary endpoint

The following sensitivity analyses will be made

- To assess the impact of the endpoints calculated from MMTT that is stopped before 4 hours due to hyperglycaemia or hypoglycaemia, a sensitivity analysis will be performed excluding these endpoints.

- To assess the impact of the endpoints calculated from MMTT profile that includes imputed values, a sensitivity analysis will be performed excluding these endpoints.
- A sensitivity analysis will be performed excluding endpoints calculated from the MMTT, where the date of the MMTT is more than one day after the last liraglutide dosing.
- An analysis using last observation carried forward (LOCF) of the primary endpoint. The analysis will be made using a normal linear regression model for the log-transformed primary endpoint with treatment, stratum and sex as fixed factors and age and baseline value (log-transformed) as covariates.
- An analysis based on the subjects completing the treatment period (i.e. completing the visit at week 54). The analysis will be made using a normal linear regression model for the log-transformed primary endpoint with treatment, stratum and sex as fixed factors and age and baseline value (log-transformed) as covariates
- In case the assumption of equal variance-covariance between the treatments turns out not to be reasonable a sensitivity analysis will be added where the variance-covariance matrix for the repeated measurements for each subject will depend on treatment.

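### The primary MMRM fits one covariance matrix to all four arms although the sample size assumes SD 1 on placebo and 0.5 on the combination, so neither the 5% level nor the 80.4% power is assured

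*SAP*

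**What the plan says.** - **Planning (SAP 2.1):** "the standard deviation is assumed to be 1 in the placebo group and 0.5 in the group treated with NNC0114-0006", the second group being NNC0114-0006 combined with liraglutide. The same section says the residual SD may differ by treatment. With 98% against 65% preservation, "then the power will be 80.4% with 60 subjects completing the trial in each of the two treatment arms". The calculation is made "using a two-sided test and 5% level of significance". No SD is given for either monotherapy arm.
- **Protocol 17.3:** the primary model's matrix was to be "unstructured and may depend on treatment, if an assumption of equal variance-covariance matrix between treatments turns out not to be reasonable".
- **SAP 2.3, after Table 2-2:** only "The variance-covariance matrix for the repeated measurements for each subject will be unstructured" remains. SAP section 3 records that the treatment-dependent option was removed from the primary analysis and gives no reason.
- **SAP 2.3, sensitivity analyses:** "In case the assumption of equal variance-covariance between the treatments turns out not to be reasonable a sensitivity analysis will be added". No test, threshold or decision-maker is named. The other sensitivity analyses concern excluded endpoints, LOCF and completers; none allows the variance to differ by arm.
- **Objective (SAP 1.1.1):** "The primary objective is to evaluate the effect of NNC0114-0006, liraglutide, and the combination of NNC0114-0006 and liraglutide, compared to placebo". All three active arms are therefore compared with placebo.

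**The concern.** The primary model makes an assumption that the sample-size section does not share. With only two arms of equal size, pooling the variance would be nearly harmless, because the pooled and arm-specific standard errors coincide. Here the variance is pooled over four arms. The standard error for combination versus placebo therefore moves with two SDs that nobody has stated, and the test may be too liberal or too conservative. The stated power belongs to a test with arm-specific variances, which the SAP no longer uses as primary. The one analysis that would reveal a problem may not be run.

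**Working it through.** **Inputs.** Preservation 98% and 65%, SDs 0.5 and 1, 60 completers per arm, two-sided 5% (SAP 2.1 and Table 2-1). Four arms randomised 1:1:1:1 (Protocol section 11). 304 randomised and 240 completing, i.e. 76 and 60 per arm (Protocol 6.1). The monotherapy SDs m1 and m2 are not in the documents; they are assumed to lie between 0.5 and 1.

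**Step 1: the plan's own power.** Difference = ln(0.98/0.65) = 0.4106. SE with each arm's own variance = sqrt((1² + 0.5²)/60) = 0.1443. A noncentral t with Satterthwaite df (86.8) gives 0.803 against the stated 0.804. All nine rows of Table 2-1 reproduce to about 0.001 in this way.

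**Step 2: the SE under a common matrix.** At week 54 the pooled variance is Vp = (1 + 0.25 + m1² + m2²)/4 and the model SE is sqrt(2Vp/60). The true SE for combination versus placebo stays at 0.1443. Using normal approximations:

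- level = 2(1 − Φ(1.96 × model SE / true SE))
- power = Φ(0.4106/0.1443 − 1.96 × model SE / true SE)
- 95% CI coverage = 1 − level

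Combination versus placebo, with m1 = m2 = m:

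| m | Vp | Model SE | Level | Power | CI coverage |
|---|---|---|---|---|---|
| 0.5 | 0.4375 | 0.1208 | 10.1% | 88.6% | 89.9% |
| 0.75 | 0.5938 | 0.1407 | 5.6% | 82.5% | 94.4% |
| 0.791 | 0.6250 | 0.1443 | 5.0% | 81% | 95.0% |
| 1 | 0.8125 | 0.1646 | 2.5% | 72.9% | 97.5% |

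The contrast is on target only when the two monotherapy variances average 0.625. The higher power in the first row is bought with an inflated level.

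**Step 3: the other contrasts.** The true SE for monotherapy versus placebo is sqrt((1 + m²)/60); its level runs from 10.1% (m = 0.5) to 7.7% (m = 1). The true SE for combination versus monotherapy is sqrt((0.25 + m²)/60); its level runs from 1.0% to 2.5%.

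**Step 4: can all three placebo contrasts be at 5%?** This needs 2Vp to equal 1.25, 1 + m1² and 1 + m2² at once, so m1 = m2 = 0.5. But then 2Vp = (1 + 0.25 + 0.25 + 0.25)/2 = 0.875, not 1.25. Under the planned SDs no pair of monotherapy SDs works. On a grid of m1 and m2 from 0.5 to 1 in steps of 0.01, the largest of the three placebo-contrast levels lies between 7.7% and 12.1%. The maximum occurs at SDs 0.5 and 1: there Vp = 0.625 and combination versus placebo is exactly at 5%, but the SD-1 monotherapy contrast has true SE sqrt(2/60) = 0.1826 against a model SE of 0.1443.

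**Step 5: simulation.** A four-arm pooled t test (236 df, 200,000 runs) gave combination-versus-placebo levels of 10.1%, 5.6%, 5.0% and 2.6% and power of 88.3%, 82.0%, 80.9% and 72.5% at m = 0.5, 0.75, 0.791 and 1. An arm-specific test held 4.9% to 5.1% for every contrast, with power 0.80. A covariate-adjusted four-arm regression (40,000 runs) gave levels of 10.1%, 5.7% and 2.7% at m = 0.5, 0.75 and 1, and 5.0% to 5.1% with arm-specific variances.

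**The case against.** The strongest counter-argument is about the null hypothesis. The plan attaches SD 0.5 to the combination as part of the alternative. If a treatment does nothing and all arms share one distribution, the common-matrix test holds 5%. The inflated levels need equal geometric means together with unequal SDs. That is correct, and it limits the claim about the level. It does not rescue the CI coverage or the stated power, which are at issue precisely when the planned SDs hold.

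The SDs are also tentative: SAP 2.1 admits limited knowledge and takes them from a published trial of another agent. At a central value of 0.75 for both monotherapies, the only powered contrast is barely affected (5.6%, 82.5%). This also stands; the 10% to 12% figures are ends of a range, not predictions.

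This is a phase 2 trial in which "No adjustment for multiple testing will be performed", so strict error control is not a design goal. Yet the SAP still commits to a 5% significance level and 95% intervals for each comparison, and those are the figures affected.

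Finally, replacing a data-dependent choice of primary model by a fixed one, before code break, improves pre-specification. Agreed, but the treatment-specific model can be fixed in advance just as well, and the data-dependent element now sits in the sensitivity analysis. Making that analysis unconditional would disclose a problem without protecting the primary test.

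**Conclusion.** The concern holds. The SAP's primary model is inconsistent with its own sample-size assumptions, and the 80.4% applies to a test with arm-specific variances. Under the planned SDs, combination versus placebo has an actual level between 10.1% and 2.5% and a rejection rate between 88.6% and 72.9% as both monotherapy SDs go from 0.5 to 1. At least one of the three placebo contrasts in the primary objective always runs at 7.7% or more.

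These figures assume 60 completers per arm, complete week-54 data and monotherapy SDs chosen for illustration. The actual four-visit model with partial data from the roughly 21% who do not complete (1 − 60/76) would shift them somewhat. If all SDs are equal there is no problem. The point is confined to the primary endpoint, since no unequal variances are stated for the others. It should be fixed before code break.

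**What to change.** In SAP 2.3, for the primary endpoint only:

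- Make a treatment-specific unstructured covariance matrix over the four post-baseline visits the primary model, with Kenward-Roger or Satterthwaite degrees of freedom.
- Name a fallback if it does not converge, for example a treatment-specific heterogeneous Toeplitz structure (4 variances + 3 correlations = 7 parameters per arm).
- Run the common-matrix model unconditionally as a sensitivity analysis and delete the conditional wording.

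The cost is SAP text and one model option before code break. The model then has 10 covariance parameters per arm, 40 in total instead of 10, with about 76 randomised and 60 completing per arm. The convergence risk is small and covered by the fallback. If the variances were in fact equal, the loss is negligible: simulated power falls from 0.848 to 0.846 with all SDs at 0.75.
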